11.2.4.4 Disease Control Rate (DCR)

The DCR is defined as the percentage of patients with a best response rate of CR, PR, or SD for at least 12 weeks. The DCR will be summarized with frequencies and percentages.

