5.1.2 Treatment Period

Lucitanib will be administered once daily and swallowed with water (see [Section 7.3](#)). Patients should take lucitanib at approximately the same time each day, on an empty stomach, at least 2 hours before and 2 hours after a meal (fasting window is a total of four hours). Treatment with lucitanib is continuous but cycles will be defined as 28 days in duration. Dosing will be delayed or reduced according to protocol-specified toxicity criteria (See [Section 7.4](#)). Protocol-specified treatment will continue until there is clinical tumor progression or unacceptable toxicity.

Patients will undergo serial assessments for anti-tumor efficacy, drug safety, and PROs. Tumor scans will be acquired by the investigative site and evaluated locally for patient treatment decisions. Electronic copies of tumor scans will be uploaded to a central radiological vendor and held for review, if deemed necessary. Sparse blood sampling for POPPK analyses will be conducted in all patients treated with lucitanib. Serial blood sampling for PD evaluation will be conducted. Local laboratories will be used for standard hematology and chemistry tests. Echocardiogram (ECHO)/multiple-gated acquisition (MUGA) will be done locally. ECGs will be stored and may be analyzed centrally. Patients will be asked to self-monitor their BP at least two times per week and instructed to contact the study site in the event of a BP reading equal or above 160 mmHg systolic and/or greater than 100 mmHg diastolic (see [Section 9.5.1.3](#)).

Patients with SD or better after their Cycle 6 scan will continue to have tumor scans every 12 ± 1 weeks until tumor progression. After discontinuation of protocol-specified treatment, subsequent specific anticancer therapy used at the investigator's discretion will be recorded. Patients will be encouraged to undergo an optional post-treatment tumor biopsy at time of progression and before subsequent-line therapy is initiated.

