9 STUDY PROCEDURES

[Table 4](#) summarizes the procedures and assessments to be performed for patients in Cohorts A, B and C with exception of patients in the PK sub study; [Table 5](#) summarizes the procedures and assessments to be performed for patients in the PK sub study.

Unless specified, all procedures and assessments are to be completed within ± 2 days of the scheduled time point and are synchronized with administration day of lucitanib.

Table 4: Schedule of Assessments (All Cohorts)

		Treatment Period (Daily Dosing) ^A						
		Cycle 1			Cycle 2 and Beyond	Cycle 2 Only		
Procedure ^B	Screening	Day 1 ^C	Day 4	Day 15	Day 1	Day 15	End-of-Study	Two Monthly Follow-Up
Informed Consent	X							
Medical/Oncology History	X							
Brief History			X	X		X		
Complete Physical Examination	X	X		X	X		X	
ECOG Performance Status	X	X			X		X	
Vital Signs, Height, Weight ^D	X	X	X	X	X	X	X	
Prior/Concomitant Medications and Procedures	X	X			X		X	
Contraceptive Counseling ^E	X						X	
Serum Pregnancy Test ^F	X						X	
Hematology, Including Reticulocytes ^G	X	X		X	X		X	
Serum Chemistry ^H	X	X		X	X		X	
Urinalysis ^I	X	X	X	X	X	X	X	
Tumor Scans (Including brain imaging for patients with known CNS metastases or when clinically indicated) ^J	X				X		X	
Submit FFPE Tumor Tissue ^K	X						X	
Adverse Events ^L	X	X	X	X	X	X	X	
Lucitanib Dispensation/Administration		X			X			
ECG Assessments ^M	X	X			X		X	
LVEF (ECHO or MUGA) ^N	X				X		X	
Plasma for ctDNA Analysis ^O	X	X		X	X		X	
Plasma PD Biomarker Sampling ^P	X	X		X	X		X	

		Treatment Period (Daily Dosing) ^A						
		Cycle 1			Cycle 2 and Beyond	Cycle 2 Only		
Procedure ^B	Screening	Day 1 ^C	Day 4	Day 15	Day 1	Day 15	End-of-Study	Two Monthly Follow-Up
Blood for Sparse PK Sampling ^Q				X	X			
Pharmacogenomic Blood Sampling		X						
Quality of Life Questionnaire ^R		X			X		X	
Review and Collection of BP and Dosing Diary		X	X		X		X	
Survival Status							X	X
Subsequent Therapies for Breast Cancer							X	X

^A Lucitanib will be administered daily, at least 2 hours before and 2 hours after a meal (on an empty stomach) with water (240 mL or 8 ounces). The total fasting period is 4 hours.

^B Unless specified, procedure is completed ±2 days of scheduled time point. Procedures for C1D4 must be completed ±1 day of scheduled time point.

^C Procedures required prior to lucitanib administration on C1D1 may be omitted if completed ≤3 days earlier during the screening period.

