9.5.2 Efficacy Evaluations

9.5.2.1 Tumor Assessments

The first on-treatment scan should be completed on Cycle 2, Day 1, and every 8 ± 1 weeks through Cycle 6 (i.e., C4D1, C6D1). Thereafter, scans should be completed every 12 ± 1 weeks (i.e., C9D1, C12D1, C15D1, etc.) until disease progression. All patients must have scans to confirm radiographic progression. Tumor scans do not need to be repeated at end-of-study if <2 weeks since last scan or the patient had disease progression at the last scan. Patients that permanently discontinue lucitanib should continue scans until radiographic disease progression. Scans will be evaluated locally for patient treatment decisions. Copies of tumor scans will be

collected centrally to facilitate independent evaluation if subsequently required. Tumor response will be interpreted using RECIST Version 1.1 ([Appendix A](#)).

Tumor assessments should consist of clinical examination and CT scans of the chest, abdomen, and pelvis with intravenous contrast and appropriate slice thickness per RECIST Version 1.1; other alternative studies (MRI and X-ray) may be performed if clinically indicated. The same methods used to detect lesions at baseline are to be used to follow the same lesions throughout the clinical study.

Brain imaging is required at baseline. Patients with brain lesions detected at baseline require repeat brain imaging as part of the follow-up tumor assessments. The same methods used to detect brain lesions at baseline are to be used to follow the lesions throughout the clinical study.

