After the end of the treatment, the need for repetitive tumor evaluations depends on whether the trial has as a goal the response rate or the time to an event (progression/death). If ‘time to an event’ (e.g., time to progression, disease-free survival, PFS) is the main endpoint of the study, then routine scheduled re-evaluation of protocol specified sites of disease is warranted. In randomized comparative trials in particular, the scheduled assessments should be performed as identified on a calendar schedule (for example: every 6–8 weeks on treatment or every 3–4 months after treatment) and should not be affected by delays in therapy, drug holidays, or any other events that might lead to imbalance in a treatment arm in the timing of disease assessment.

Confirmatory Measurement/Duration of Response

Confirmation

As ORR is not the primary endpoint, confirmation of response is not required.

Duration of Overall Response

The duration of overall response is measured from the time measurement criteria are met for CR or PR (whichever is first recorded) until the first date that recurrent or PD is objectively documented (taking as reference for PD the smallest measurements recorded since the treatment started).

The duration of overall CR is measured from the time measurement criteria are first met for CR until the first date that recurrent disease is objectively documented.

Duration of Stable Disease

SD is measured from the start of the treatment (in randomized trials, from date of randomization) until the criteria for progression are met, taking as reference the smallest measurements recorded since the treatment started (if the baseline sum is the smallest, this is the reference for calculation of PD).

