## 12.2.2 Disease Control Rate (DCR)

The DCR is defined as the percentage of patients with a best response rate of CR, PR, or SD for at least 12 weeks. The DCR will be summarized with frequencies and percentages.

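### Whether stable disease followed by progression at the week-12 scan counts as disease control depends on the day of that scan, and the disease control rate tends to read high

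*Protocol*

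**What the plan says.** Protocol 11.2.4.4 counts a patient as having disease control on a "best response rate of CR, PR, or SD for at least 12 weeks". SAP 12.2.2 repeats this and adds nothing: "The DCR is defined as the percentage of patients with a best response rate of CR, PR, or SD for at least 12 weeks". Neither section says how the 12 weeks is established, whether a scan at week 12 must show SD, or how the scan window is handled.

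SD duration is defined in one place, under Duration of Stable Disease in Protocol Appendix A, as follows: "SD is measured from the start of the treatment (in randomized trials, from date of randomization) until the criteria for progression are met". The clock stops at the date of progression, not at the last scan that showed SD.

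On the schedule, Protocol 5.1.2 states that "cycles will be defined as 28 days in duration". Protocol 9.5.2.1 states that "The first on-treatment scan should be completed on Cycle 2, Day 1", and that scans then follow "every 8 ± 1 weeks through Cycle 6 (i.e., C4D1, C6D1").

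**The concern.** The 12-week threshold sits on the nominal day of the second on-treatment scan. A patient whose only evidence of stability is the week-4 scan, and whose next scan shows progression, reaches the threshold if that scan is on time or late. The same patient with the same tumor, scanned earlier but still within the window, does not.

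Two things follow. An individual's DCR status can turn on appointment timing. And the rate can include patients who were never shown to be free of progression at 12 weeks, which pushes it upward. In a single-agent study without a control arm, a reader will naturally take the reported DCR as the share of patients whose disease was held for 12 weeks.

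**Working it through.** The plan states no DCR figure, target or power, so there is nothing to reproduce. The check has three steps.

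**1. Schedule.** With 28-day cycles, C2D1 is 28 days after C1D1 (week 4) and C4D1 is 3 × 28 = 84 days after C1D1 (exactly 12 weeks). The allowed week either side gives 77 to 91 days.

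**2. Share of patients with PD at C4D1 who count as controlled.**

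- Scanned on the nominal day: 100%.
- Scan days uniform over 77 to 91 days (assumption): 84 to 91 is 8 of 15 days, or 53%. If days are counted with the 1+ convention used for PFS in Protocol 11.2.4.1, it is 9 of 15, or 60%.
- Under the general visit window in Protocol Section 9, "within ± 2 days of the scheduled time point", the days run from 82 to 86. That gives 3 of 5 (60%), or 4 of 5 (80%) with the 1+ convention.
- PK sub-study patients, if treatment start is read as the Day -7 dose: that dose is at least 7 days before C1D1 (Protocol 9.5.5), so even a scan at 77 days falls at least 77 + 7 = 84 days after it. All count.

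**3. Size.** Progression first seen at C4D1 is taken as S(4 wk) − S(12 wk), under an assumed exponential PFS:

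S(w) = exp(−λw / 4.348), where 4.348 = 365.25 / (12 × 7) weeks per month and λ = ln 2 / median in months (or −ln 0.40 / 6 for a 6-month rate of 40%).

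The PFS levels come from the documents. The 4-month median and the 40% rate are the benchmarks in Protocol 11.3. The 9.4 months is the first-in-human breast cancer result in Protocol 3.6.1.2, treated here as a median. The last two columns multiply the difference by 8/15 and by 1.

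| Assumed PFS | S(4 wk) | S(12 wk) | Difference | Shift, uniform scan days | Shift, all at or after 84 days |
|---|---|---|---|---|---|
| Median 9.4 months | 0.934 | 0.816 | 0.119 | 0.063 | 0.119 |
| Median 4 months | 0.853 | 0.620 | 0.233 | 0.124 | 0.233 |
| 6-month PFS 40% | 0.869 | 0.656 | 0.213 | 0.114 | 0.213 |

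(Differences use unrounded values.) At a 4-month median, DCR would read 0.620 + 0.124 = 74% up to 0.620 + 0.233 = 85%, against 62% if a non-PD scan at C4D1 were required. The group in question is 0.233 × 80, or about 19 of 80 patients.

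**Sensitivity.** Patients already in CR or PR at week 4 count under either rule, if the 12 weeks attaches only to SD. If they were 25% of the group, the 4-month shift becomes 0.75 × 0.124 = 0.093 to 0.75 × 0.233 = 0.175.

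**The case against.** The strongest answer is in Protocol Appendix A, under Best overall response: all time points. There, SD as a best response must also satisfy the protocol's minimum time from baseline. The text gives nearly this case: SD at the first assessment, PD at the second and the minimum not met is a best response of PD. A patient lost after one SD assessment is inevaluable. This can be read as asking when SD was documented. On that reading, SD at week 4 then PD at C4D1 is PD, and the problem disappears. The reading is available, so a reader who infers that the plan definitely counts these patients goes further than the documents do. But the text does not say how the minimum is measured, its example turns on SD duration, and duration is defined only under Duration of Stable Disease. Neither DCR section settles the matter.

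The size is also open to challenge, and much of that challenge stands:

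- The 4-month median is a threshold for further study, not an expected value. The 9.4-month figure gives about half the shift.
- The model treats every progression between weeks 4 and 12 as found at C4D1 in a patient with SD. Early responders, deaths and unscheduled progression before C4D1 reduce the effect.
- Uniform scan days are an assumption. If scans ran systematically early, the shift would be smaller than the lower figures.
- Patients with only non-measurable disease are eligible, and Appendix A Table 9 prefers non-CR/non-PD to SD for them. They may not count at all, which lowers DCR. That is a separate gap, but the net direction across all gaps is not established.

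Finally, dating progression to the scan that shows it is also how PFS works. That is sound for PFS; the difficulty arises only when the same date certifies 12 weeks of stability.

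**Conclusion.** The point holds. Read with the only definition of SD duration, the DCR wording makes status depend on which side of 84 days the C4D1 scan falls, and the dependence works upward. The stricter Appendix A text shows that another reading exists; it does not show that the plan adopts it.

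The size rests on assumptions, because the documents give no expected DCR. With exponential PFS and scan days from uniform over the window to all on or after 84 days, the shift is roughly 6-12 points at a 9.4-month median and 12-23 points at a 4-month median. It is less with early responders, or with deaths or progression before C4D1.

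A reader might infer that the trial's efficacy conclusion is compromised. The documents do not support that. DCR is a secondary endpoint summarized by frequencies and percentages with no decision rule, and the criteria in Protocol 11.3 use median PFS and the 6-month PFS rate. The change should be made, but the primary PFS analysis does not depend on it.

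**What to change.** In Protocol 11.2.4.4 and SAP 12.2.2, state that:

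- SD of at least 12 weeks requires a tumor assessment without PD at the scheduled C4D1 scan, anywhere within its allowed window, or later.
- SD followed by PD at the C4D1 scan is not disease control.
- Timing is counted from C1D1 for all patients, including PK sub-study patients dosed on Day -7.

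Identify the scan by visit, not by a cut at 77 days. If the 8 ± 1 weeks runs from the previous scan, a C2D1 scan two days early (26 days) followed by a scan 7 weeks later (49 days) falls at 26 + 49 = 75 days. That scan would be compliant, and a 77-day cut would discard it, which brings the dependence on scan timing back.

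The cost is a sentence or two in each document, using scans already planned, and a lower reported DCR.

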11.2.4.5 Overall Survival (OS)

OS is defined as 1+ the number of days from the date of first dose of study drug to death due to any cause. Patients without a documented date of death will be censored on the last date the patient was known to be alive. OS will be summarized utilizing Kaplan-Meier methodology.

11.2.4.6 PK Sub-Study

Comparative PK parameters will include AUC_{0-t} , C_{max} , T_{max} , $T_{1/2}$, V_{SS}/F , and Cl/F for lucitanib and will be determined using noncompartmental methods. AUC_{0-t} will be calculated using the trapezoid rule. The PK parameters will be compared between the tablet and the capsule formulations.

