3.6.1.1 Pharmacokinetics

The clinical PK properties of lucitanib were evaluated within the FIH study following single and multiple daily oral administrations. Lucitanib exposure exhibited high inter-patient variability. Lucitanib was rapidly absorbed with a maximum plasma concentration (C_{max}) reached within 1–3 hours. In the dose-escalation phase, exposure to lucitanib increased with increasing dose with no evidence of non-linearity. The $t_{1/2}$ of lucitanib was long (31–40 hours) and in agreement with the low apparent clearance and the moderate apparent volume of distribution. The moderate apparent volume of distribution is the result of high plasma protein binding limiting the distribution but a high permeability. At steady state, the area under the curve from time zero to 24 hours (AUC_{0-24}) was approximately double that on Day 1, consistent with daily administration of a compound with a $t_{1/2}$ of 31–40 hours.

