^J Tumor scans obtained within 21 days prior to C1D1, may be used as the baseline scans. Scans should preferably be CT scans of the chest, abdomen, and pelvis with intravenous contrast and appropriate slice thickness per RECIST Version 1.1, using the same methods throughout the study that were used to detect lesions at baseline. Other alternative studies (MRI, X-ray) may be performed if clinically indicated. Brain imaging is required at baseline and must be repeated at follow-up tumor assessments for patients with brain lesions. The first on-treatment scan should be completed on C2D1, and every 8 \pm 1 weeks through Cycle 6 (i.e., C4D1, C6D1). Thereafter, scans should be completed every 12 \pm 1 weeks (i.e., C9D1, C12D1, C15D1, etc.) until disease progression. Tumor scans do not need to be repeated at End-of-Study if < 2 weeks since last scan or the patient had disease progression at the last scan. Scans will be evaluated locally for patient treatment decisions. Scans will be sent to a central radiological laboratory.

^K For patient selection, *FGFR1* and 11q amplification status may be determined based on local assessment, or based on central assessment as confirmed by a prescreening process. FFPE tumor tissue is required for all enrolled patients. The post-treatment biopsy is optional and requires additional consent. Detailed sample handling instructions are provided in the Laboratory Manual.

^L AEs will be assessed from the time of first dose of lucitanib through 28 days after the last dose.

^M On Day -7 a dose of the lucitanib tablet formulation will be given followed by a dose of the lucitanib capsule formulation on Day 1.

^N ECGs will be taken in triplicate anytime during screening, pre-dose (5–10 mins prior to dosing), and approximately 2 hr (± 5 min) post-dose on Day -7 (Cohort C) and Day 1 (All Cohorts) of each Cycle, and at End-of-Study, any time after treatment is discontinued.

^O LVEF will be assessed by ECHO or MUGA. It is recommended to use the same technique for a given patient throughout the study. ECHO should be performed at Screening, on C2D1, and every 8 weeks thereafter, and at the End-of-Study.

^P Whole blood will be collected pre-dose and processed locally for plasma ctDNA. Collections occur at screening, C1D1, C1D15, Day 1 of all subsequent Cycles, and End-of-Study. Refer to the Laboratory Manual for sample handling instructions.

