9.5.5 PK Sub Study

Up to 20 patients will participate in the PK sub study. PK sampling will be performed at specified time points on each on the following two days:

- Day –7: lucitanib in tablet formulation
- Day 1: lucitanib in capsule formulation

The dose assigned for patients participating in the PK sub study will be the same for Days -7 and 1 and depends on the version of the amendment approved at the time of patient enrollment (Amendment #3: 15 mg; Amendment #4: 10 mg).

The total time from the Day -7 visit to the Cycle 1 Day 1 visit must not be fewer than 7 days, but may be greater than 7 days, if necessary. Lucitanib will not be taken between Day -7 and Cycle 1, Day 1.

PK specimens will be taken on Day -7 and Day 1 PK specimens will be collected 5–10 min pre-dose, and post-dose at 15 (± 2) min, 30 (± 3) min, 1 hr (± 5 min), 1.5 hr (± 5 min), 2.5 hr (± 10 min), 4 hr (± 15 min), 6 hr (± 15 min), 8 hr (± 15 min), 10 hr (± 30 min) (optional), and 24 hr (± 30 min). Refer to the Laboratory Manual for sample handling instructions.

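### PK sub-study: the fixed-order tablet-capsule comparison has no carry-over correction, and 24-hour sampling is too short to compare t1/2, Cl/F and Vss/F reliably between formulations

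*Protocol*

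**What the plan says.** - **Order.** Protocol Section 9, Table 5 footnotes: on Day -7 "a dose of the lucitanib tablet formulation will be given followed by a dose of the lucitanib capsule formulation on Day 1". No sequence is randomised.
- **Gap.** Protocol 9.5.5: the interval between the two visits "must not be fewer than 7 days, but may be greater than 7 days, if necessary", and "Lucitanib will not be taken between Day -7 and Cycle 1, Day 1".
- **Sampling.** Protocol 9.5.5: a pre-dose sample on each day, then samples to 24 h, with the 10 h sample optional. By the synopsis (Study Treatment), dosing goes on from Cycle 1 Day 2.
- **Half-life.** Protocol 3.6.1.1: the half-life "of lucitanib was long (31–40 hours) and in agreement with the low apparent clearance". The same section says that steady-state AUC0-24 "was approximately double that on Day 1".
- **Analysis.** Protocol 11.2.4.6 and SAP 12.2.4 name all six parameters, use noncompartmental methods with a trapezoid AUC, and end: "The PK parameters will be compared between the tablet and the capsule formulations". Neither mentions carry-over, the Day 1 pre-dose level or a period effect.
- **Qualifier.** The synopsis (twice), Protocol 4.2.2 and SAP Table 1 make the parameters conditional on adequate data. Protocol 11.2.4.6 and SAP 12.2.4 do not, and no document says what adequate means.

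**The concern.** Two features of the analysis do not fit the drug's kinetics.

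First, because the order is fixed, leftover tablet drug always falls in the capsule profile. The resulting error in the tablet/capsule AUC ratio has a known sign, and averaging over up to 20 patients does not reduce it. The sample that measures the residue is already scheduled but is given no role in the analysis.

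Second, t1/2, Cl/F and Vss/F depend on the terminal phase, and sampling ends before one half-life has passed. The tablet has a late point by accident, in the Day 1 pre-dose sample. The capsule has none and cannot have one, because daily dosing follows. A comparison of these parameters would set a moderately informed estimate against a very noisy one.

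This is a stated secondary objective. Protocol 7.2 also lets patients start on, or switch to, tablets once PK comparability is judged acceptable. Noisy terminal estimates could suggest a difference that is not there, or hide one that is.

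**Working it through.** The documents give no sample-size, precision or margin figure for the sub-study, so there is no planned figure to reproduce.

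**Inputs.** Half-life 31–40 h, Tmax 1–3 h and accumulation of about 2 (Protocol 3.6.1.1); minimum gap 168 h and last sample 24 h (Protocol 9.5.5). Assumed: first-order one-compartment kinetics and equal formulations.

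**Formulas.** Half-lives elapsed = 168/t1/2. Residual fraction = 2^(−168/t1/2). Share of AUCinf seen by 24 h = 1 − 2^(−24/t1/2). Accumulation = 1/(1 − 2^(−24/t1/2)).

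| | t1/2 = 31 h | t1/2 = 40 h |
|---|---|---|
| Half-lives in 168 h | 5.4 | 4.2 |
| Residual fraction | 2.3% | 5.4% |
| Added to capsule AUC0-24 (oral model, Tmax 1–3 h) | 2.4% | 5.5–5.6% |
| Tablet/capsule AUC ratio seen when truth is 1.00 | 1/1.024 = 0.98 | 1/1.056 = 0.95 |
| Half-lives covered by 24 h | 0.77 | 0.60 |
| AUC0-24 as share of AUCinf (oral model) | 41% | 33–34% |
| Extrapolated | 59% | 66–67% |
| Accumulation implied (simple formula) | 2.4 | 2.9 |

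Five half-lives equal 168 h at t1/2 = 168/5 = 33.6 h, so the minimum gap is shorter than five half-lives only above that value.

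**Check against the accumulation statement.** Setting accumulation to exactly 2 gives 2^(−24/t1/2) = 0.5, so t1/2 = 24 h. The gap is then 7 half-lives and the residue is 2^(−7) = 0.8%. AUC0-24 would still be only half of AUCinf.

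**Precision of an individual t1/2.** Log-linear fits to simulated profiles, 100,000 per setting. The documents give no residual error, so it is varied. The figures are the 5th to 95th percentiles.

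| True t1/2 | Error | Samples at 6, 8, 24 h | Adding 10 h |
|---|---|---|---|
| 31 h | 5% | 25–42 h | 25–42 h |
| 31 h | 10% | 20–66 h | 20–64 h |
| 40 h | 5% | 30–61 h | 30–60 h |
| 40 h | 10% | 24–124 h | 24–120 h |

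At 15% error and a true 40 h, about 5% of profiles show no decline at all. With points at 24 h and 168 h, available only for the tablet, the range at 10% error and a true 40 h is about 37–44 h.

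**Does the carry-over correction depend much on the terminal rate?** The amount to subtract from AUC0-24 is Cpre × (1 − 2^(−24/t1/2)) × t1/2/ln 2. At 31 h this is Cpre × 0.415 × 44.7 = 18.6 × Cpre. At 40 h it is Cpre × 0.340 × 57.7 = 19.6 × Cpre. An error in t1/2 across that range changes a correction of a few per cent by only about one-twentieth of itself.

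**The case against.** The case for leaving the plan alone has real parts.

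- **The washout is not clearly short.** It is above five half-lives at 31 h, and 168 h is only a minimum. This stands: a reader might infer that the gap is always under five half-lives, and the documents do not say so.
- **Carry-over is small.** It is 2–6% at most on the stated range and about 0.8% on the accumulation figure. No comparability margin is given, so nothing shows that a decision would change. This stands as a limit on importance, but it does not justify ignoring an error of known direction that a planned sample can measure.
- **Slow eliminators.** One could assume a 60 h half-life and obtain about 15% carry-over. Protocol 3.6.1.1 does report high variability between patients, but of exposure, not of half-life. That case has no support in the documents and is not relied on here.
- **The data-adequacy qualifier already covers the terminal parameters.** It appears in both documents, and in the synopsis it directly precedes the formulation comparison. This stands in part: the condition exists, but it is absent from both analysis sections and has no criterion, while the shortfall can be foreseen from the protocol's own half-life.
- **The tablet switch.** A reader might infer that it depends on t1/2 or Cl/F. Protocol 7.2 names no parameter, so this cannot be claimed. AUC0-t, Cmax and Tmax are observed within 24 h and remain usable.
- **Late-point assumptions.** Using the Day 1 pre-dose sample assumes a quantifiable level (about 2–6% of Cmax) and a single decay rate across an unsampled 24–168 h gap. This stands. The documents give no assay limit.

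**Conclusion.** The concern holds in a limited form. With the order fixed and no correction specified, capsule AUC0-24 is inflated by about 2–6% at the minimum gap, or about 0.8% if the effective half-life is near 24 h, always in the capsule's favour. With about 59–67% of AUCinf extrapolated and no possible late sample for the capsule, t1/2, Cl/F and Vss/F cannot be compared reliably between formulations. The comparison of AUC0-24, Cmax and Tmax remains usable within patient, subject to a period effect that this design cannot separate from formulation.

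The extrapolation result needs only the stated half-life and first-order kinetics. The carry-over figures also assume equal formulations and a gap at the minimum. The t1/2 ranges depend on an assumed residual error: for a true 40 h, about 30–60 h at 5% and 24–120 h at 10%.

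**What to change.** In Protocol 11.2.4.6 and SAP 12.2.4:

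1. Correct each capsule profile by subtracting the Day 1 pre-dose concentration, when quantifiable, decayed from time zero at the patient's own terminal rate. Show the uncorrected result alongside.
2. Base the tablet-versus-capsule comparison on within-patient ratios of corrected AUC0-24 and Cmax, plus Tmax.
3. Remove t1/2, Cl/F and Vss/F from the between-formulation comparison. Report them descriptively where the data are adequate, with the Day 1 pre-dose sample, at its actual time, as a late point for the tablet.
4. State that the fixed order leaves formulation confounded with period. Steps 1–3 do not remove this.

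**Cost.** Wording changes in the protocol as well as the SAP, with no added sample, visit or patient. Three parameters listed under the comparative PK objective leave the comparison.
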